1.0 BACKGROUND

1.1 Background and Significance

Cancer is one of the leading causes of death in the United States, accounting for nearly one out of every four deaths each year. According to the American Cancer Society, the lifetime risk for developing cancer is approximately one in three for women and one in two for men; of those diagnosed, one in four men and one in five women will ultimately die.¹

Cancer patients are particularly vulnerable to nutritional depletion as a result of the joint impact of the malignant disease process and its treatment.² The frequency of weight loss and malnutrition in oncology patients has been estimated to range from 31 to 87 percent.³ Among most types of cancer, weight loss has been associated with a decreased ability to perform activities of daily living (ADLs), and even a six percent weight loss has been found to predict a diminished response to treatment, survival, and quality of life.⁴ Weight change and associated performance status are important, as they can potentially influence decisions about modality, dosage, and timing of treatment(s).

Malnutrition has been given the definition of "a state of nutrition in which a deficiency or excess (or imbalance) of energy, protein, and other nutrients causes measurable adverse effects on tissue/body form (body shape, size and composition) and function and clinical outcome."⁵ Many studies examining the consequences of malnutrition in the oncology population have revealed increased morbidity and mortality rates when compared to well-nourished patients.⁶ It has been proposed that cancer patients often die from malnutrition and its related complications rather than from the direct effects of the disease itself.⁷ Thus, the identification of oncology patients at nutritional risk and implementation of nutritional intervention is critical to ultimately reduce cancer morbidity and mortality.⁸

In addition to malnutrition, the oncology population often suffers from a cachexia syndrome. Cancer cachexia is a term which is given to patients who have ongoing loss of skeletal muscle mass, insulin resistance, along with other nutritional and medical abnormalities. It is characterized by an "ongoing loss of skeletal muscle mass (with or without loss of fat mass) that cannot be fully reversed by conventional nutritional support and leads to progressive functional impairment".⁹ Typically, cachexia is first seen when a patient experiences anorexia. The consequence of the anorexia can affect the patient and caregivers in many different ways including, physical, psychological, social, and existentially. The patients and caregivers often feel negative emotions with regards to cachexia and malnutrition.¹⁰ Some of these negative emotions are described as "sadness, disappointment, bewilderment, confusion, bother, concern, dissatisfaction, feeling upset, anger, frustration, guilt, desperation, anguish, fear, anxiety, and existential distress".¹¹ This stress is not only on the oncology patient but the caregiver as well.

There is no single cause of the symptoms associated with cancer cachexia despite years of research. Along with the causes, there is not one particular treatment plan for this syndrome. Jointly there are three main interventions which are pertinent in treating and managing cancer cachexia. These are antitumor treatment, nutrition intervention, and pharmaceutical intervention.

Nutrition assessment and intervention of patient is one of the most crucial steps in a patient's care. Nutritional assessment of cancer patients can reveal mild or moderate states of malnutrition before the patient becomes visibly wasted.¹²⁻¹⁸ With in-depth nutritional assessment, performed by an RD or medical professional, the presence of symptoms that may adversely affect nutritional status is documented, which enables the planning of appropriately individualized interventions. Early and intensive nutrition intervention provides beneficial outcomes in terms of positive impact on nutrition status, physical function, quality of life, weight maintenance, and overall survival in oncology patients. Poor nutritional status at baseline is associated with worse outcomes that may aggravate from both disease course and its treatments, thus oncology patients at risk for malnutrition should receive early, regular and individualized nutrition intervention and support.¹⁹⁻²³

Many pharmacological agents have been studied in order to help prevent deterioration of patients. However, many of the results remain variable. Some studies have found there may be a benefit in terms of appetite but limited increase in lean body mass and continued weight loss in patients despite medicine administration. However, overall improved quality of life (QOL) may be possible for these patients. There is not currently one pharmacologic agent which has been proven to be beneficial for the general oncology population.²⁴

With anorexia being a major symptom of cancer cachexia and the psychological stress which impacts the patient and caregivers, and limited research showing the benefit of both nutrition intervention and pharmacological agents on overall survival and lean body mass, our goal to is focus on decreasing the suffering and distress associated with eating in our patients.

2.0 AIMS

2.1 Aim 1

- To establish the feasibility of implementing an algorithm for nutrition interventions in our Cancer Center

2.2 Aim 2

- To assess associations between appetite scores and general quality of life measures in cancer patients.

3.0 METHODS/DESIGN

The patients must fulfill the following inclusion criteria prior to entering the study.

3.1 Inclusion Criteria

1. Patients with a diagnosis of head/neck, lung, pancreatic cancer, or metastatic disease of any solid primary malignancy
2. Planned, ongoing, or recently treated patient (within the past 30 days) with radiation therapy, chemotherapy, immunotherapy, and/or intravenous targeted biologic therapy
3. No previous use of appetite stimulants (steroid use for purposes other than appetite stimulant is allowed)
4. All patients must sign study specific informed consent prior to being included in the study
5. No contraindication to appetite stimulants

4.0 METHODS/DESIGN

4.1 Patient Selection

Patients with head/neck, lung, pancreatic cancer or metastatic disease of any solid primary malignancy will be screened for the study using the Oncology Nutrition Assessment which is currently the Standard of Care in the Montefiore Einstein Center for Cancer Care (Appendix 1). The patients will then be informed regarding the study and decide to join or not. The patients who wish not to be included will be asked as to why if open to answer.

4.2 Study Design

Appetite Assessments

This study will utilize the validated Council of Nutrition appetite questionnaire (CNAQ) (Appendix 2) to evaluate the effect of the nutrition intervention and pharmacological agents on patients'

appetite and nutritional intake. The CNAQ has been used in many studies as a validated questionnaire to assess appetite. The patient populations in these studies have ranged from community-dwelling adults and nursing home residents to patients with chronic diseases like ALS.²⁵⁻²⁶ It has also been used as a validated analysis of appetite in studies with patients with liver cancer in Taiwan and head and neck cancer.²⁷⁻²⁸

The patients will fill out this questionnaire weekly to assess change. If the patient scores >28 on the CNAQ, then the questionnaire will be administered biweekly, as will the nutrition education.

Quality of Life Assessments

All participants will also be asked to complete a quality of life survey (Functional Assessment of Cancer Therapy-General Population (FACT-GP), Appendix 3) on a weekly or biweekly basis at the same time as the nutrition assessment. If a patient is not present in the Medical Oncology or Radiation Therapy at the time either assessment is due, the assessments will be performed over the phone.

FACT-GP measures quality of life by asking about physical, function, emotional, and social wellbeing. In its creation, the questionnaire was modified to so it can be applicable to the general cancer population. It has been used to assess quality of life in many different sites of cancer.²⁹⁻³³

Nutritional Status

Nutritional status will be determined based on the answers to the appetite assessment and quality of life questionnaire, as well as the nutrition assessment provided by the Registered Dietitian. No lab values will be used to assess nutrition status during the course of this study.

Algorithm

The patient care will follow a pathway based on their responses to the CNAQ and clinical judgment of the physician and dietitian. The patients with fair-good appetite (score on CNAQ >24) will not receive any pharmacological agents and will receive nutrition intervention alone. Nutrition intervention will be in accordance with the Academy of Nutrition and Dietetics guidelines. The intervention will involve “purposefully planned action(s) designed with the intent of changing a nutrition-related behavior, risk factor, environmental condition, or aspect of health status”³⁴.

The patients with poor-fair appetite (score on CNAQ <24) will be provided nutrition intervention by the Registered Dietitian and then put into one of three pharmacological groups. If the patient’s prognosis is extremely poor (<12 weeks expected survival, based on discussion with the patient’s treating physicians) and there is no additional disease modifying therapy planned, the patient will be prescribed 4mg dexamethasone (which is FDA approved), once daily, to be taken orally in the morning. Dexamethasone is given to patients with a limited expected lifespans because it has been found to be effective on a short-term basis. Also, the long-term usage of steroids has been found to myopathy and other various side effects.³⁵

If a patient has a history of marijuana use or has tried it in the past, then he/she will be prescribed medical marijuana based on financial availability due to previous exposure exhibiting better tolerance to the drug. If the marijuana is not feasible, he or she will be prescribed dronabinol (which is FDA approved). Dronabinol is used as a substitute as it contains synthetic delta-9-tetrahydrocannabinol (THC), a substrate of marijuana and therefore has a similar affect to medical marijuana. Since dronabinol is compounded similarly to medical marijuana, then for this patient population the tolerance to the medication is likely to be good.³⁶⁻³⁸

If the patient does not have any history of marijuana use, mirtazapine will be prescribed. Mirtazapine has been show to improve both appetite and quality of like in cancer patients.³⁹⁻⁴¹ Dosing mirtazapine was determined by guidelines published by the US Department of Veterans Affairs/Department of Defense. If the patient is under the age of 70, then she/he would be prescribed 15mg of mirtazapine (which is FDA approved), once daily, to be taken orally at bedtime. For geriatric population (if the

patient is over the age of 70), then she/he would be prescribed 7.5mg of mirtazapine, once daily to be taken orally at bedtime.

Refer to the flowchart (Appendix 4) for the sample pathway.

Study Duration

The study period will begin after the initial screening and immediately following study registration and last for three months.

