5.0 STATISTICAL CONSIDERATIONS

Primary Endpoint:

The primary endpoint of the study is administration of the appropriate nutrition/pharmaceutical intervention, as defined by our algorithm, within 30 days of study enrollment. A secondary and exploratory endpoint is to assess associations between appetite scores and general quality of life measures.

Statistical Analysis:

Descriptive statistics (eg: counts, percentages) will be used to report each of the following measures:

- number of potential subjects screened
- number of potential subjects who met inclusion criteria
- number of subjects consented/enrolled
- study subject demographics
- number of subjects completing baseline assessments
- number of subjects receiving nutritional intervention following the study algorithm
- number dropped out will be presented as frequency counts and percentages along with their 95% confidence intervals

Associations between appetite scores and quality of life will be examined using analysis of variance (for continuous scale variables) and Cochran Mantel Haenzsel testing (for categorical variables). Changes in quality of life scores over time will be examined using covariance pattern models or linear mixed models, as appropriate.

Sample Size Justification:

This is a pilot study to examine the feasibility of implementing our nutritional intervention algorithm in the study population. We have based the sample size on precision in estimating the rate of feasibility. We hypothesize that we will be successful in implementing the algorithm in 85% of the study population. We will recruit a total of 30 participants, which would produce a 95% confidence interval around our point estimate of the feasibility rate whose width is 28% (i.e. 67% to 95%), based on the exact (Clopper-Pearson) formula.

Exploratory Secondary Endpoints:

Descriptive statistics will be utilized to characterize quality of life measures over time for study subjects and to characterize the frequency of outpatient IV fluid hydration episodes, Emergency Room visits, and hospital admissions in study subjects.

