Diarrhea: Yes/No

Feel full quickly: Yes/No

Fatigue: Yes/No

Ostomy: Yes/No

Open wound or ulcer: Yes/No

Visible cachexia/muscle wasting: Yes/No

Trouble buying food: Yes/No

Assessment Completed (Auto-Calculation):

Referral to Nutritionist

Referral:

Appendix 2

Council on Nutrition Appetite Questionnaire

- 1) My appetite is
 1. Very poor
 2. Poor
 3. Average
 4. Good
 5. Very good

- 2) When I eat, I feel full after
 1. Eating only a few mouthfuls
 2. Eating about a third of a plate/meal
 3. Eating over half of a plate/meal
 4. Eating most of the food
 5. Hardly ever

- 3) I feel hungry
 1. Never
 2. Occasionally
 3. Some of the time
 4. Most of the time
 5. All of the time

- 4) Food tastes
 1. Very bad
 2. Bad
 3. Average
 4. Good
 5. Very good

- 5) Compared to when I was younger, food tastes
 1. Much worse
 2. Worse
 3. Just as good
 4. Better
 5. Much better

- 6) Normally, I eat
 1. Less than one regular meal a day
 2. One meal a day
 3. Two meals a day
 4. Three meals a day
 5. More than three meals a day (including snacks)

7) I feel sick or nauseated when I eat

1. Most times
2. Often
3. Sometimes
4. Rarely
5. Never

8) Most of the time my mood is

1. Very sad
2. Sad
3. Neither sad nor happy
4. Happy
5. Very happy

TOTAL SCORE: _____

Scoring Total the score by adding the numbers associated with the patient's response. A score of less than 28 is cause for concern. If the total is 8-16, the patient is at risk for anorexia and needs nutrition counseling. 17-28, the patient needs frequent reassessment. >28, the patient is not at risk at this time.

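### Does leaving a CNAQ score of exactly 24 outside both written branches undermine the feasibility endpoint?

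*Combined protocol and SAP*

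**What the plan says.** Section 4.2 (Algorithm) splits patients by CNAQ total. On one side, "The patients with fair-good appetite (score on CNAQ >24) will not receive any pharmacological agents"; they have nutrition intervention only. On the other, "The patients with poor-fair appetite (score on CNAQ <24) will be provided nutrition intervention by the Registered Dietitian" and are then placed in one of three drug groups. The split is introduced by a more general statement: "The patient care will follow a pathway based on their responses to the CNAQ and clinical judgment of the physician and dietitian". The description of the algorithm closes with "Refer to the flowchart (Appendix 4) for the sample pathway".

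The reassessment interval has its own cut: "If the patient scores >28 on the CNAQ, then the questionnaire will be administered biweekly". The scoring key in Appendix 2 says "Total the score by adding the numbers associated with the" patient's responses, and places 24 inside a wider band: "17-28, the patient needs frequent reassessment".

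Section 5.0 names as primary endpoint "administration of the appropriate nutrition/pharmaceutical intervention, as defined by our algorithm, within 30 days of study enrollment". It plans 30 participants, expects 85% success, and gives an exact 95% interval of 67% to 95%. Section 7.4 has the CNAQ score and the medication recorded at each visit.

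**The concern.** Above 24 means no drug and below 24 means a drug, so a patient at exactly 24 meets neither condition. The appetite labels do not help, because both include fair. Appendix 2 has no cut at 24 and no rule on drugs.

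The pilot exists to find out whether the algorithm can be carried out. If the algorithm does not say what should happen at 24, it also does not say whether giving or withholding a drug there is a success. Clinicians might treat such patients differently, or the side might be chosen after the data are in.

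The mirtazapine wording has a similar feature: one instruction is for patients under 70 and another for those over 70.

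**Working it through.** **The plan's own figure.** The Clopper-Pearson limits are the 0.025 quantile of Beta(x, n − x + 1) and the 0.975 quantile of Beta(x + 1, n − x). With n = 30 and x = 0.85 × 30 = 25.5, they are 67.3% and 95.3%, width 28.1 points. This matches Section 5.0. The neighbouring whole counts give 65.3% to 94.4% (25/30) and 69.3% to 96.2% (26/30).

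**Can 24 occur?** Appendix 2 has eight items scored 1 to 5, so totals are integers from 8 × 1 = 8 to 8 × 5 = 40. Answering 3 throughout gives 8 × 3 = 24. It can occur.

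**What is unsettled at 24?**
- Nutrition intervention: settled, since both branches include it.
- Reassessment interval: settled as weekly, since only totals above 28 move to biweekly.
- Drug or no drug: not settled by the Section 4.2 prose.

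**How many patients?** The documents give no CNAQ distribution, so this step rests on an assumption: roughly normal totals with mean m from 22 to 32 and SD s from 4 to 6. Then P(24) = Φ((24.5 − m)/s) − Φ((23.5 − m)/s).
- Smallest: m = 32, s = 4 gives 0.0136, and 30 × 0.0136 = 0.4 patients.
- Largest: m = 24, s = 4 gives 0.0995, and 30 × 0.0995 = 3.0 patients.

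**Effect on the rate.** One patient is 1/30 = 3.3 points. Start from 26/30 = 86.7% (69.3% to 96.2%) with every patient at 24 counted as a success, then recount them:

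| Patients at 24 | All counted as failures | Drop | All excluded | Drop |
|---|---|---|---|---|
| 1 | 25/30 = 83.3% (65.3–94.4) | 3.3 | 25/29 = 86.2% (68.3–96.1) | 0.5 |
| 2 | 24/30 = 80.0% (61.4–92.3) | 6.7 | 24/28 = 85.7% (67.3–96.0) | 1.0 |
| 3 | 23/30 = 76.7% (57.7–90.1) | 10.0 | 23/27 = 85.2% (66.3–95.8) | 1.5 |

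The failure columns are the extreme. They require 24 to be assigned afterwards to the side opposite to what the clinician did, for every such patient. Even so, 83.3%, 80.0% and 76.7% all lie inside the starting interval of 69.3% to 96.2%.

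**Does any decision turn on it?** Section 5.0 sets no minimum feasibility rate and no test of the rate. The result is a percentage with an interval.

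**The case for a change.** The best case for a change is that the algorithm is what this study tests, so its branches are the scoring standard and should cover every possible score. Clinical judgment is offered as a general input, not as a rule for ties. The flowchart is called only a sample pathway, so it may not override the prose. Under the assumptions above, and with patients independent, the chance of at least one patient at 24 is 1 − (1 − 0.0136)^30 = 34% at the low end and 1 − (1 − 0.0995)^30 = 96% at the high end. Assigning 24 would take one line.

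Part of this stands. The prose is incomplete at 24, such a patient may well turn up, and the text does not expressly say that judgment breaks the tie.

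The harm to the endpoint does not follow. Section 5.0 refers to the algorithm, not to the Section 4.2 prose alone, and that section itself points to Appendix 4. The flowchart is absent from the text available here, so it cannot be presumed silent. If it is silent, a natural reading is that judgment decides where the score does not, and either choice then follows the algorithm. If that reading is refused, the Section 7.4 records identify the patients concerned, and the rate can be shown under each handling. The link to a primary endpoint also holds only under Section 5.0, because Section 4.3 names quality of life as primary.

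The age wording is weaker still. Someone some months past a seventieth birthday can be read as over 70, so a gap for all 70-year-olds appears only if age means completed years.

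**Conclusion.** This is a drafting slip at one score value, and it calls for no change to the plan. No stated rule gives a wrong result: the prose is silent on the drug component at a total of 24, and clinicians and analysts have sensible ways to fill that silence. Writing down a side would bring no better method of analysis and would leave sample size, data collection and the interval as they are.

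The effect is at most 3.3 points per affected patient, and 0.5 to 1.5 points in total if one to three such patients are excluded. Both are small beside a planned interval of 28 points. The count of 0.4 to 3.0 patients rests on the assumed score distribution, and the larger drops of 6.7 and 10.0 points rest on every such patient being scored against the care given.

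Which side 24, or age 70, falls on is a clinical matter for the sponsor, and no view is taken here. If the flowchart and the prose proved to disagree, they would have to be reconciled as a matter of drafting. Nothing in the visible text shows that they do.

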4.3 Primary Study Endpoint

The primary endpoint of this study is assessing the impact on quality of life for the oncology patients by using an algorithm for nutrition intervention and appetite stimulants.

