4.4 Exploratory Secondary Study Endpoints

- Hydration administration in the clinics
- Emergency Room visits
- Hospital admissions and days spent in the hospital

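### Sections 4.3 and 5.0 name different primary endpoints, quality of life and delivery of the intervention within 30 days; neither takes precedence and only the second is sized

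*Combined protocol and SAP*

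**What the plan says.** Section 4.3, the protocol's own primary endpoint section, reads: "The primary endpoint of this study is assessing the impact on quality of life for the oncology patients", through use of the algorithm for nutrition intervention and appetite stimulants. It gives no instrument, time point, summary measure or target.

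Section 5.0 reads: "The primary endpoint of the study is administration of the appropriate nutrition/pharmaceutical intervention, as defined by our algorithm, within 30 days of study enrollment". The next sentence there is: "A secondary and exploratory endpoint is to assess associations between appetite scores and general quality of life measures".

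The sample size paragraph in section 5.0 describes the study this way: "This is a pilot study to examine the feasibility of implementing our nutritional intervention algorithm in the study population". It then says: "We have based the sample size on precision in estimating the rate of feasibility". The inputs are 30 participants, an expected success rate of 85%, and an exact (Clopper-Pearson) 95% interval of 67% to 95%, width 28%.

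Quality of life over time appears twice more in section 5.0. Under the statistical analysis: "Changes in quality of life scores over time will be examined using covariance pattern models or linear mixed models, as appropriate". Under the exploratory secondary endpoints: "Descriptive statistics will be utilized to characterize quality of life measures over time for study subjects".

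Section 4.4 lists three exploratory secondary endpoints: hydration, Emergency Room visits, and the item "Hospital admissions and days spent in the hospital". Quality of life is not among them. Aim 1 (section 2.1) is feasibility of the algorithm. Aim 2 (section 2.2) is the association of appetite scores with quality of life.

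**The concern.** The two statements concern different variables: a patient-reported score, and a yes/no measure of whether care was delivered. Each is called the primary endpoint in the singular. Both are current text, and section 6.2 requires the study to be run as the approved protocol describes, so both cannot be followed.

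A report that follows section 4.3 would lead with a change in quality of life that was never sized and has no control group, and would call it an impact of the algorithm. A report that follows section 5.0 would lead with feasibility and depart from section 4.3. If neither is settled beforehand, the main result could be whichever looks better: feasibility if the delivery rate is high, quality of life if FACT-GP scores rise.

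**Working it through.** **1. Which parts of the document support which primary**

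| Place | Quality of life as primary | Delivery within 30 days as primary |
|---|---|---|
| 2.1 Aim 1 | no | yes (feasibility) |
| 2.2 Aim 2 | no; association with appetite only | no |
| 4.3 | yes | no |
| 5.0 Primary Endpoint | no; association is secondary and exploratory | yes |
| 5.0 Sample Size Justification | no | yes (feasibility rate) |
| 5.0 Exploratory Secondary Endpoints | no; quality of life over time is placed here | no |

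Section 4.3 is the only place that makes quality of life primary. The sample size text does not repeat the 30-day window, but it plainly refers to the section 5.0 endpoint. No sentence sets an order of precedence.

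**2. Reproducing the stated sizing**

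Inputs from section 5.0: n = 30, p = 0.85, so x = 0.85 × 30 = 25.5; two-sided 95% interval.

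Clopper-Pearson limits: lower = 0.025 quantile of Beta(x, n − x + 1); upper = 0.975 quantile of Beta(x + 1, n − x).

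- x = 25.5: Beta(25.5, 5.5) gives 67.26% and Beta(26.5, 4.5) gives 95.33%. Width 28.07 points. This matches the stated 67% to 95%, width 28%.
- x = 25 (83.3%): 65.28% to 94.36%, width 29.08 points.
- x = 26 (86.7%): 69.28% to 96.24%, width 26.97 points.

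At 85% the Wald interval (72.2% to 97.8%) and the Wilson interval (68.4% to 93.7%) do not match, so the plan used the exact method it names. The figure is right, and it belongs to the binary endpoint of section 5.0.

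**3. Sizing of the section 4.3 endpoint**

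The documents give no SD, effect size, time point or target precision for FACT-GP, so there is no figure to reproduce. For scale only, assume one pre-post change per patient, a two-sided 5% level, and results in SD units of the change score. The 95% half-width is t(0.975, n − 1)/√n; the detectable mean change at 80% power comes from the noncentral t distribution.

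| Evaluable patients (20 and 24 are assumed) | Half-width (SD) | Detectable at 80% power (SD) |
|---|---|---|
| 30 | 0.37 | 0.53 |
| 24 | 0.42 | 0.60 |
| 20 | 0.47 | 0.66 |

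The plan makes no statement about whether such precision is adequate.

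**4. Whether the endpoint lists resolve the conflict**

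Section 5.0 names five secondary or exploratory items: the appetite/quality-of-life association, quality of life over time, hydration, Emergency Room visits and hospital admissions. Section 4.4 lists the last three. The two it omits (5 − 3 = 2) are the two that concern quality of life, so section 4.4 does not settle its status.

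**5. Whether the design supports the word *impact***

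Section 4.2 puts all participants on one pathway, with no comparison group. Section 3.1 admits patients before, during or up to 30 days after anticancer treatment, so FACT-GP may move for reasons unrelated to the algorithm. The planned covariance pattern or mixed model can describe the change. It cannot assign a cause.

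**The case against.** The strongest reply is that section 4.3 is one unaligned sentence. The statistical section defines a binary endpoint with a time window, sizes it, and calls quality of life exploratory. Aim 1 and the pilot statement agree, and the study is a 30-patient single cohort with no success threshold. On this view the intent is clear, and choosing the primary after the fact is a possibility that nothing in the documents shows to have been planned.

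It stands that feasibility was probably intended. But that is inference, and section 4.3 is where a reader looks for the primary endpoint. Pilot status explains why quality of life has no power calculation; it does not reconcile two primaries.

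Some narrower objections have merit:

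- The absence of quality of life over time from section 4.4 may simply follow from section 4.3 calling quality of life primary. It is part of the same conflict and not a further fault.
- Section 4.4 includes days in hospital, while section 5.0 summarizes only the frequency of admissions. This is a separate mismatch.
- Section 4.2 also speaks of the effect of the intervention on appetite. That wording is a separate point.
- The spreadsheet in section 7.4 has no stated field for delivery of the nutrition intervention. Section 5.0 already commits to counting patients who receive intervention per the algorithm, so aligning section 4.3 adds no new data need.
- Section 4.2 leaves a CNAQ score of exactly 24 and an age of exactly 70 unassigned. Those passages must be reconciled in their own right before every patient can be scored on the section 5.0 endpoint. The gap exists whichever section governs.

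**Conclusion.** The concern holds and should be corrected before analysis. The plan names two incompatible primary endpoints with no rule of precedence. One is sized, and its interval reproduces (67.3% to 95.3%, width 28.1 points). The other has no sizing input of any kind, and without a comparator its change over time cannot be read as an impact of the algorithm.

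The conflict itself rests on the text and needs no assumption. The SD-unit figures for quality of life rest on the assumptions stated with them and are for scale only. That feasibility is the intended primary is a reading of Aim 1, the pilot statement and the sample size basis; the documents do not say so outright.

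**What to change.** - **Section 4.3:** replace the text with the section 5.0 endpoint as the single primary: intervention per the algorithm delivered within 30 days of enrollment, reported as a proportion of enrolled patients with an exact 95% interval. Section 5.0 speaks of the study population, so taking enrolled patients as the denominator is a clarification the sponsor should confirm.
- **Section 4.4:** keep the three listed items and add two as secondary or exploratory. The first is change in FACT-GP score over time, analyzed with the covariance pattern or linear mixed model already planned and worded as change, not impact. The second is the association between appetite scores and quality of life.
- **Section 5.0, exploratory secondary endpoints paragraph:** refer to the planned model as well as the descriptive summaries.

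The cost is wording in three places. N = 30, its 67% to 95% interval and the planned models stay as they are, and section 7.4 already records the FACT-GP score and assessment date at each visit. The price is that quality of life can no longer be presented as the primary result. If the sponsor does want it as primary, section 4.3 would have to define the score, time point and summary measure, and the endpoint would need its own sizing.
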